4.2.4. Elimination from Per-protocol analysis Set (PPS)

All the elimination codes used for the mFAS are applicable and in addition the codes reported in the Table below.

Table 4Elimination codes from PPS

Code	Condition under which the code is used	Visit (timepoints) where the code is applicable
1040	Administration of concomitant vaccine(s) forbidden in the protocol	All
1050	Randomisation failure (e.g., subject assigned to wrong stratum, subject randomized out of order)	All
1060	Randomisation code was broken (study blinding/unblinding procedures)	All
1070	 Study treatment not administered per protocol: wrong route; correct treatment administered but not compatible with treatment regimen associated to treatment schedule; wrong treatment/replacement administered; 	All
	 wrong treatment repracement administered, treatment administered with a Staph aureus infection ongoing Study treatment not prepared as per protocol (e.g. reconstitution) 	
1080	Vaccine temperature deviation	All
1090	Expired vaccine administered	All
2010	Eligibility criteria not met	All
2040	Administration of concomitant medication(s) forbidden in the protocol	All
2050	Not withdrawn after developing withdrawal criteria other than prohibited concomitant vaccination/medication – forbidden medical condition	All
2060	Not withdrawn after developing withdrawal criteria other than prohibited concomitant vaccination/medication infection related to the vaccine	All
2080	Subjects did not comply with the vaccination schedule	All

Code	Condition under which the code is used	Visit (timepoints) where the code is applicable
2120	Obvious incoherence, abnormal serology evolution or error in data (incoherence between CRF and results, wrong sample labelling)	All
2130	testing performed on samples not aligned with ICF; Subjects bled but not supposed to be bled	All

4.2.5. Elimination from unsolicited and solicited safety set

4.2.5.1. Unsolicited Safety Set

All the elimination codes used for the ES are applicable and in addition the code 1150.

Code 1150 will be attributed to subjects if all the following conditions are met:

- subject did not return for visit/perform phone contact on Day 8 and Day 68 (only for groups 4 and 5)
- subject did not complete the eDiary;
- subject did not perform the scheduled phone contact 30 days after vaccinations;
- subject did not return for the visit scheduled 12 months after last vaccination and did not perform the phone contact scheduled 6 months after last vaccination;
- subject did not report any unsolicited AE.

4.2.5.2. Laboratory Safety Set

The analysis for haematology and biochemistry parameters will be performed on a subset of the Unsolicited Safety Set. All the elimination codes used for the Unsolicited Safety Set are applicable and in addition the code:

- 2100 (no safety serological results available)
- 2110 (incorrect or expired sample tube used for sample type-safety blood draw)

An additional analysis excluding subjects with safety blood samples out of window will be performed (elimination code for the specific analysis: 2090 applicable to V2 for groups 1-3, V2, V5 for group 4 and V2, V6 for group 5).

Note: in the PoP phase, subjects in Step 2 are not included in this set.

4.2.5.3. Solicited safety set

All the elimination codes used for the ES are applicable and in addition the code:

- 1160 (no post-vaccination solicited safety data excluding30 minutes, during 7 days of follow up)
- 1161 (post-vaccination solicited safety data excluding 30 minutes, during 7 days of follow up not reported according to GCP)

4.2.5.4. Solicited safety set 30m

All the elimination codes used for the ES are applicable and in addition the code:

• 1160b (no post-vaccination solicited safety data during 30 minutes after the vaccination)

4.2.5.5. Overall Safety Set

All subjects who are in the Solicited Safety Set 30m and/or in the Solicited Safety Set and/or in the Unsolicited Safety Set (code 2150 for subjects with no safety follow up beyond the day of vaccination).

Subjects will be analysed as "treated" (i.e., according to the vaccine a subject received rather than the vaccine to which the subject may have been randomized).

5. STATISTICAL ANALYSES

The standard data derivation rules and stat methods are described in section 10.1 while the study specific data derivation rules and statistical methods are described in section 9 of this document.

5.1. Demography

5.1.1. Analysis of demographics/baseline characteristics planned in the protocol

Demographic characteristics (age at first study vaccination in years, gender, race and ethnicity), SSTIs history (PoP only), will be summarised by overall and vaccine groups using descriptive statistics:

- Frequency tables will be generated for categorical variables such as centre.
- Mean, standard deviation, median, minimum and maximum will be provided for continuous data such as age, height, weight and body mass index (BMI).

Withdrawal status will be summarized by group using descriptive statistics:

- The numbers of withdrawn subjects will be tabulated according to the reason for withdrawal (specifying if there is any relationship with COVID-19.)
- The number of subjects enrolled into the study as well as the number of subjects excluded from the per protocol set (PPS) and mFAS will be tabulated.

5.1.2. Additional considerations

Demographic characteristics will also be summarized on Enrolled Set for web public disclosure.

Vital signs will be summarized by vaccine group using descriptive statistics at all timepoint(s) the information is collected on Exposed Set and modified Full Analysis Set.

Summary of important protocol deviations leading to elimination will be tabulated by vaccine group and by relationship with COVID-19. An individual listing will also be provided.

Summary of medical history will be performed on Exposed Set by Medical Dictionary for Regulatory Activities (MedDRA) and Preferred Term.

5.2. Exposure

5.2.1. Analysis of exposure planned in the protocol

Any impact of COVID-19 on subjects' exposure will be tabulated by vaccine group.

5.2.2. Additional considerations

The number and percentage of subjects who received study vaccine doses will be tabulated for each study group (based on the ES).

5.3. Efficacy/Effectiveness

5.3.1. Analysis of efficacy planned in the protocol

The efficacy analysis will be based on the mFAS. A supplementary analysis will be based on the PPS.

Rules for SSTI cases:

- All cases of SSTI will be reported, including multiple cases in the same subject.
- The start date of a case is the date of the visit during which the diagnosis is done by a treating physician or equivalent licensed medical professional or based on medical records review by a study physician.

• A new SSTI episode may be assessed by a study physician at site for any SSTI visit occurring after the clinical resolution of the previous SSTI and, if it does not represent a persistence of the previous episode as per medical judgement, it can be considered a new episode.

Endpoint	Statistical Analysis Methods
Key secondary	The analysis of efficacy will be based on the occurrence of the first case of SSTI anytime from 14 Days after the administration of the second dose of the study vaccine up to 12 months. All subjects from the mFAS will contribute to the comparison between the treatment and the placebo groups.
	Time to occurrence of key secondary endpoint during the defined efficacy follow-up period will be compared between groups by calculating the respective Hazard ratio
	Vaccine (VE) will be defined as 1 minus the hazard ratio times 100:
	$VE = (1 - hazard ratio) \times 100$
	Censoring will occur at the time of the last scheduled or medically attended visit without the occurrence of SSTI cases before the end of follow up. Subjects who will complete the follow up without events will be censored at 1 year.
	In order to check the statistical significance, 1-sided P-value for the log rank test will be calculated. 1-sided nominal type I error will be 1.61% at the interim analysis and 5.89% at the final analysis. The objective will be met if the 1-sided P-value calculated for the null hypothesis H0 = [occurrence SSTI VE = 0%] is lower than defined 1-sided alpha level.
Co- secondary	The co-secondary endpoint will be analysed only if the statistical significance is demonstrated for the key secondary endpoint.
	For this analysis, the FAS will account for the first case of SSTI anytime from 14 Days after the administration of the first dose of the study vaccine up to 14 months.
	Time to occurrence of the co-secondary endpoint during the defined efficacy follow-up period will be compared between groups by calculating the respective Hazard ratio. In order to check the statistical significance, 1-sided P-value for the log rank test will be calculated. 1-sided nominal type I error will be 5.89%. (the nominal alpha level is equal to the key secondary at the final analysis, because we use a sequential procedure). The objective will be met if the 1-sided P-value calculated for the null hypothesis H0 = [occurrence SSTI VE = 0%] is lower than defined 1-sided alpha level.
	If statistical significance for key secondary endpoint is not demonstrated, a descriptive analysis of co-secondary endpoint will be provided.

Table 5 Statistical analysis methods for the secondary study objectives

CONFIDENTIAL 208833 (STAPH AUREUS BIOCONJ-001 STG) Statistical Analysis Plan Amendment 5

Statistical Analysis Plan Amenoment 5

CCI			

CCI			

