# 10. STATISTICAL CONSIDERATIONS

## 10.1. Sample size determination

#### 10.1.1. Hypotheses related to primary and secondary objectives

For the primary safety objective no statistical hypotheses are applicable.

Two statistical hypotheses will be tested for the secondary efficacy objective.

- 1. Null Hypothesis : Hazard Ratio (HR) ≥1 after the second vaccination Alternative Hypothesis: HR <1
- 2. Null Hypothesis : Hazard Ratio (HR) ≥1 after the first vaccination Alternative Hypothesis: HR <1

If the first hypothesis is statistically significant, also the second hypothesis will be tested in a sequential procedure. In case the first hypothesis is not significant no conclusions will be taken with respect to the second hypothesis. Both hypotheses will be tested using the log rank test.

For the first hypothesis referring to the key efficacy endpoint two sequential analyses will be done following a Group Sequential Design using the O'Brien-Fleming spending function (with 48% and 100% of the total planned events). *(Amended 6 October 2022)* 

At the interim analysis the first hypothesis will be tested spending 1.61% alpha and 8.83% beta (this means a power equal to about 91%). At the final analysis the alpha will be 5.89% and the beta 11.17% (this means a power equal to about 89%). Overall after two sequential analyses the cumulative alpha will be 7.5% and the cumulative beta 20% (or power equal to 80%).

The assumptions to test the first hypothesis on the HR after the second vaccination are:

- to observe an HR (hazard ratio) equal or below to 0.39
- a true incidence rate for the SSTI equal to 0.07 (starting to count the events two weeks after the second dose)
- time to event follows an exponential distribution.

The second hypothesis of the secondary vaccine efficacy objective will be tested for all the events occurring after the first vaccination, with one-sided alpha equal to 5.89% and power 89% (both adjusted error values will be retrieved from the second group sequential test performed on the first hypothesis).

The following assumptions are made to test the hypothesis on the HR after the first dose of vaccine/placebo:

- to observe an HR below 0.43
- a true incidence rate equal to 0.12 (starting to count the events two weeks after the first dose)
- time to event follows an exponential distribution

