## 10.1.2. Sample size calculation

The incidence rates of *S. aureus* SSTI (index cases and recurrences) at the selected study centre(s) are difficult to predict. For this reason, the study is designed as an event driven trial and includes **CO**. After the dose-escalation safety lead-in epoch and the PoP staggered enrolment step of PoP vaccination epoch are concluded and no safety issues are found, enrolment will continue with a randomisation of 1:1 ratio either to the *S. aureus* candidate vaccine or to the placebo group. It is estimated that approximately 500 to 600 subjects will be needed to achieve the **CO** 

The key objective of clinical efficacy will be measured counting culture confirmed cases of recurrent *S. aureus* SSTIs occurring from 14 days after the second dose up to 12 months after the second dose. Before the second dose has elicited a proper response (i.e. from Day 61 to Day 75) subjects will be also monitored for SSTI.

The event driven design includes **CCL** (culture confirmed *S. aureus* SSTI recurrences) overall after the second dose to test the null hypothesis of no efficacy assuming an HR equal to 0.39 from Day 75 (14 days after the second vaccination) up to 12 months after the second vaccination.

The study sample size is not fixed and the enrolment will proceed until reaching the planned number of events necessary to evaluate the first statistical hypothesis of no efficacy (HR $\geq$ 1) with an overall power equal to 80% and an overall one-sided alpha equal to 7.5%.

A group sequential design with the O'Brien Fleming spending function is applied to the first hypothesis after the second vaccination, CCL

After the final analysis for the first hypothesis a sequential procedure will be used in order to control the overall type I error for the efficacy objective: starting from the first hypothesis on the efficacy after the second dose, the second hypothesis on the efficacy after the first dose will be tested only if the efficacy after two doses will be demonstrated.

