#### 10.3.3.1. Case accountability:

Rules for SSTI cases:

- All cases of SSTI will be reported, including multiple cases in the same subject.
- The start date of a case is the date of the visit during which the diagnosis is done by a treating physician or equivalent licensed medical professional or based on medical records review by a study physician.
- A new SSTI episode may be assessed by a study physician at site for any SSTI visit occurring after the clinical resolution of the previous SSTI and, if it does not represent a persistence of the previous episode as per medical judgement, it can be considered a new episode.

| Endpoint     | Statistical Analysis Methods  |
|--------------|---|
| Kev          | The analysis of efficacy will be based on the occurrence of the first case of SSTI anytime from 15    |
| secondary    | Days after the administration of the second dose of the study vaccine up to 12 months. All            |
|              | subjects from the mFAS will contribute to the comparison between the treatment and the placebo        |
|              | groups.   |
|              | Time to occurrence of key secondary endpoint during the defined efficacy follow-up period will be     |
|              | compared between groups by calculating the respective Hazard ratio (methods will be detailed in       |
|              | the SAP).   |
|              | Vaccine (VE) will be defined as 1 minus the hazard ratio times 100:                                   |
|              | VE = (1 – hazard ratio) x 100   |
|              | Censoring will occur at the time of the last scheduled or medically attended visit without the        |
|              | occurrence of SSTI cases before the end of follow-up. Subjects who will complete the follow-up        |
|              | without events will be censored at 1 year.  |
|              | In order to check the statistical significance, 1-sided P-value for the log rank test will be         |
|              | calculated. 1-sided nominal type I error will be 1.61% at the interim analysis and 5.89% at the final |
|              | analysis. The objective will be met if the 1-sided P-value calculated for the null hypothesis H0 =    |
|              | [occurrence SSTI VE =0%] is lower than defined 1-sided alpha level.                                   |
| Co-secondary | The co- secondary endpoint will be analysed only if the statistical significance is demonstrated for  |
| _            | the key secondary endpoint.   |

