7.2. Statistical considerations for interim analyses

One interim analysis for efficacy and futility will be done following a group sequential design for the key secondary efficacy analysis. The interim analysis is event driven and is planned when 48% of the assumed total number of culture confirmed cases of recurrent *S. aureus* SSTIs (13 events after the second vaccination) will be observed and it may stop the enrolment of the study for efficacy or futility.

In case of stopping for efficacy at the interim analysis, also the second secondary efficacy endpoint will be tested with the same alpha used for the first hypothesis (alpha=1.613%). Enrolment maybe stopped if the null hypothesis is rejected (efficacy) or accepted (futility) after the interim analysis, but the follow up of subjects will continue for 12 months after the second dose.

The design assumes that 2 sequential tests are made for the key efficacy objective using test boundaries (binding for efficacy and not binding for futility) calculated by the O'Brien-Fleming spending function and assuming that time to event follows an exponential distribution. An adjusted alpha equal to 1.613 % and a beta equal to 8.83% (or a power equal to 91%) will be spent at the interim to reject or accept the null hypothesis for the key efficacy objective with a sample of 13 cases. At the final analysis the adjusted alpha and beta will be, respectively, 5.89% and 11.17% (or a power equal to 89%) with a sample of 27 cases. The final alpha and beta after the two sequential tests will be kept to 7.5% and 20%. The secondary efficacy endpoint will be tested at the final analysis after rejecting the null hypothesis for the key objective.

The proc SEQDESIGN is used for the planning of the test boundaries with the code reported in the section 5.3. The output with the limits is used in the proc SEQTEST (see section 5.3.2)

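### The final-look cut-off of 5.89% is the alpha spent at stage 2, not a nominal p-value level; the design's own boundary is p < 0.069

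*SAP*

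**What the plan says.** SAP 5.3.1, Table 5, gives the rule for the key secondary endpoint: "1-sided nominal type I error will be 1.61% at the interim analysis and 5.89% at the final analysis". The objective is met if the one-sided log-rank p-value falls below that level. Protocol 10.3.3.1 has the same rule: "1-sided nominal type I error will be 1.61% at the interim analysis and 5.89% at the final" analysis. The co-secondary rows carry 5.89% over as the nominal level of the key endpoint.

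The design sections use the same figures differently. Protocol 10.1.1 describes an "O'Brien-Fleming spending function (with 48% and 100% of the total planned events") and concludes: "Overall after two sequential analyses the cumulative alpha will be 7.5% and the cumulative beta 20% (or power equal to 80"%). Protocol 10.1.2 repeats "an overall one-sided alpha equal to 7.5"%. SAP 7.2 spends "An adjusted alpha equal to 1.613 % and a beta equal to 8.83% (or a power equal to 91"%) at 13 events, then 5.89% and 11.17% at 27 events, and states: "The final alpha and beta after the two sequential tests will be kept to 7.5% and 20"%. It takes the boundaries from SEQDESIGN and adds: "The output with the limits is used in the proc SEQTEST".

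**The concern.** Alpha spent at a look and the nominal level at that look coincide only at the first look. At the second, the increment is the probability of crossing there without having crossed before. Part of the nominal tail belongs to trials that already stopped, so the nominal level must exceed the increment. Using the increment as the cut-off treats the two looks as if they never reject together.

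The plan then contains two final success rules: the Table 5 p-value, and the O'Brien-Fleming boundary of SAP 7.2. They disagree for some results, and this is the threshold for the trial's only confirmatory objective. Choosing between them after unblinding would be post hoc. A similar slip affects beta: the increments 8.83% and 11.17% are restated as stage powers of 91% and 89%.

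**Working it through.** **Inputs.** One-sided alpha 7.5%, power 80%, HR 0.39, looks at 48% and 100% of events (Protocol 10.1.1); 13 and 27 events, interim alpha 1.613%, efficacy boundary binding, futility non-binding (SAP 7.2). Assumed: normal approximation with corr(Z1, Z2) = √t, and 1:1 allocation.

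**1. Reproduce the plan's figures.** Classical O'Brien-Fleming shape: z1 = C/√t, z2 = C, with C solved from

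P(Z1 > z1) + P(Z1 < z1, Z2 > z2) = 0.075.

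At t = 0.48, √t = 0.693:
- C = 1.4835, so z1 = 1.4835/0.6928 = 2.141.
- Interim alpha = P(Z > 2.141) = 1.613%. Stage-2 increment = 7.5% − 1.613% = 5.887%.
- With a futility boundary of the same shape and 80% power, the drift is 2.420 and the beta increments are 8.83% and 11.17%.
- Events = 4 × 2.420² / (ln 0.39)² = 26.4, rounded up to 27.

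All stated figures reproduce. This shows that 5.89% is the increment.

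**2. Nominal level that spends this increment.** P(Z > 1.483) = 0.069. It is 0.0690 for both t = 0.48 and t = 13/27 with an interim level of 1.613%.

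**3. What the written rule spends.** p < 0.0589 means z2 = 1.564. Then P(Z1 < 2.141, Z2 > 1.564) = 4.94%, and the total is 1.61% + 4.94% = 6.56%.

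**4. Power at HR 0.39.** Drift = (√27/2) × 0.9416 = 2.446 at 27 events and (√13/2) × 0.9416 = 1.698 at 13.

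| | p < 0.069 | p < 0.0589 |
|---|---|---|
| Overall one-sided alpha | 7.50% | 6.56% |
| Power, 27 events, futility not acted on | 83.7% | 81.7% |
| Power, 27 events, futility obeyed | 80.7% | 79.1% |
| Power at the design drift (26.4 events), futility obeyed | 80.0% | 78.3% |
| Critical HR, exp(−2z/√27) | 0.565 | 0.548 |

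**5. Can a real result fall between the thresholds?** The first 40 subjects are allocated 3:1. The vaccine share is (30 + 230)/500 = 0.520 or (30 + 280)/600 = 0.517. For 10 vaccine and 17 placebo cases, with a score approximation that carries this share into the analysis set:
- N = 500: expected 14.04, variance 6.739, z = 1.556, p = 0.060.
- N = 600: expected 13.95, variance 6.743, z = 1.521, p = 0.064.

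Both lie between 0.0589 and 0.069. Under exact 1:1 the same split gives p = 0.089 and 9 versus 18 gives 0.042, so this example depends on the 3:1 step.

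**6. Choice of boundary.** The Lan-DeMets O'Brien-Fleming spending function would spend about 1.0% at the interim, with a nominal final level of about 7.2%. The plan's numbers come from the classical boundary. Under neither is 5.89% the nominal final level.

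**The case against.** The strongest reply is that the consequence is small and partly an artefact of normal theory. A split of 1.61% + 5.89% is a valid Bonferroni-type rule and cannot exceed 7.5% nominally. With only 27 events the log-rank test is discrete. In simulated event-driven trials (assumed accrual 10 to 40 per month, futility ignored), type I error was 7.7% to 8.0% under 5.89% and 7.8% to 8.2% under 6.9%. Power under 5.89% was about 80.5% to 81%, close to the 80% target. A two-stage binomial check at N = 500 to 600 gives 8.8% to 9.4% type I error if a 10 versus 17 split rejects, and 4.3% to 4.6% if it does not. The boundary-comparison rule in SAP 7.3 covers only the interim, and the SAS code is redacted, so the programmed final boundary cannot be seen. A footnote to the testing-sequence figure says an adjusted alpha can only be given at analysis.

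Much of this stands. The error is conservative in normal theory, and 6.56% should not be read as the realised size. The contradiction does not depend on the redacted code: SAP 7.2 says that both tests of the key objective use O'Brien-Fleming boundaries with 7.5% in total, while Table 5 fixes a cut-off that does not match. The footnote gives no final boundary. The simulated power difference is larger than normal theory suggests: 83.0% against 79.3% with futility obeyed and 85.7% against 81.1% with it ignored (4,000 trials, assumed accrual 20 per month).

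**Conclusion.** The success rule is wrong as written. The 5.89% is the stage-2 alpha increment, and the nominal final level for the stated design is 0.069. By normal theory the written rule costs 1.6 to 2.0 points of power and leaves 0.94 points of the 7.5% unspent (7.50% − 6.56%). In the simulations the power cost is about 4 to 5 points and the realised type I error is near 7.5% to 8% under either cut-off, so the practical loss is power and an ambiguous decision rule. The interim level is unaffected. A success declared under Table 5 would not be undermined. The risk is a result that crosses the design boundary and is recorded as a failure, or argued over afterwards. The normal-theory figures assume 1:1 allocation and looks at 13 and 27 events; the simulated ones depend on the assumed accrual.

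**What to change.** In SAP 5.3.1 (Table 5), SAP 7.2 and Protocol 10.1.1 and 10.3.3.1:

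- Label 1.61% and 5.89% as alpha spent at each look, and 8.83% and 11.17% as beta spent. Remove the stage powers of 91% and 89%.
- State the final rule as the group sequential boundary: z > 1.483, nominal one-sided p < 0.069 at 13/27 events, recomputed in SEQTEST from the alpha actually spent and the observed event counts. A fixed p-value cannot follow a change in counts, and SAP 7.1 allows fewer than 27 events if enrolment stops after the interim.
- Name the boundary that produced the numbers (classical O'Brien-Fleming), or re-derive them if the Lan-DeMets function is meant.
- Reword the co-secondary text so that it no longer calls 5.89% the nominal level of the key endpoint.

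This is wording only and adds no patients. Overall alpha stays at 7.5% by normal theory. Because the test is discrete at 27 events, the sponsor should report the simulated type I error alongside the new threshold and not assume that it is exactly 7.5%.
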